10.3 Clinical Laboratory Data

Clinical hematology, chemistry, and urinalysis are tested at screening, check-in (Day -1 or Day 1), and Day 2/ET.

For clinical laboratory tests data, baseline is defined as the last non-missing value obtained before dosing. The predose assessment will be performed either on Day -1 or

Protocol 405-201-00037

Day 1 depending on investigator's decision. If the predose assessment is missing, the baseline value will be based on the screening visit.

Clinical laboratory tests (observed and change from baseline data) will be summarized by time point and mode of administration (intact capsules or capsule contents sprinkled on a tablespoon of applesauce). The incidence of potentially clinically relevant clinical laboratory tests as defined in [Appendix 1](#) will be summarized by mode of administration. Laboratory results that are potentially clinically relevant will also be listed out by subjects.

When laboratory test is repeated, the last repeat value will be used in the summary for that visit. Unscheduled laboratory data will not be summarized in the change from baseline table but will be included in incidence table.

10.4 Vital Sign Data

Vital signs, including systolic and diastolic blood pressure and heart rate, will be assessed at check-in, predose (within 2 hours before dosing) on Day 1, and 3 hours postdose on Day 1.

The baseline of vital sign is defined as data collected within 2 hours before dosing on Day 1. If a parameter is missing on Day 1 then the screening data collected at check-in will be used.

Change from baseline in vital signs will be summarized for post-baseline assessment. The incidence of potentially clinical relevant vital signs, as defined in [Appendix 2](#) will be summarized by time point and mode of administration. Vital sign data that are potentially clinically relevant will also be listed out by subject.

When vital sign is repeated, the last repeat value will be used in the summary for that visit. Unscheduled vital sign data will not be summarized in the change from baseline table but will be included in incidence table.

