1.3 Schedule of Assessments

Assessment	Screening ^a	Check-in ^b	Treatment	Discharge	Follow-up Telephone Call ^c	Notes
	Day -21 to Day -2	Day -1	Day 1	Day 2/EoT/ET	Day 8 (+ 2)	
Screening						
Informed consent/assent	X					Section 10.1.2
Inclusion/exclusion criteria check	X					Section 5.2
Demographic information	X					
Medical history	X					
Height	X					Section 8.7.2
Serology (HIV, HBsAg, anti-HCV)	X					
Breath or urine alcohol test and urine drug screen	X					Section 10.2
Urine pregnancy test (for FOCBP)	X	X	X ^d	X		Section 10.3
Trial Residency						
Check-in ^b		X	X			
Meals			X			Section 6.1
Discharge from clinic			X ^e	X ^e		
IMP Administration						
Centanafadine			X			Section 6.1
Safety and Tolerability						
Record AEs	X	X	X	X	X	Section 8.8
Record concomitant medications	X	X	X	X	X	Section 6.5
Body weight	X	X	X ^d	X		Section 8.7.2
Physical examination	X	X	X ^d	X		Section 8.7.2
Vital signs	X	X ^f	X ^f	X		Section 8.7.3
12-lead ECG	X	X	X ^d	X		Section 8.7.4
Serum chemistry, hematology, and urinalysis	X	X	X ^d	X		Section 8.7.1

Protocol 405-201-00037

Table 1.3-1 Schedule of Assessments

Assessment	Screening ^a	Check-in ^b	Treatment	Discharge	Follow-up Telephone Call ^c	Notes
	Day -21 to Day -2	Day -1	Day 1	Day 2/EoT/ET	Day 8 (+ 2)	
C-SSRS	X	X	X ^d	X		Section 8.7.5
Pharmacokinetics						
Centanafadine [REDACTED] plasma concentrations			X	X		Section 8.2.1
Other Procedures						
[REDACTED]			[REDACTED]		[REDACTED]	[REDACTED]

anti-HCV = hepatitis C antibodies; FOCBP = females of childbearing potential; HBsAg = hepatitis B surface antigen.

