8.7.3 Vital Signs

Vital signs (include systolic and diastolic blood pressure and heart rate) will be collected at the time points described in the schedule of assessments ([Table 1.3-1](#)). Subjects should be monitored for potentially clinically significant vital signs values ([Section 10.6](#)).

Blood pressure and heart rate measurements will be made in the supine and standing positions after the subject has been in each position for at least 3 minutes. The supine measurements will be performed first followed by the standing measurements.

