10.5 Physical Examination Data

A complete physical examination will be performed at screening, check-in (Day -1 or Day 1), and Day 2/ET. A complete physical examination will consist of measurement of height and weight and an assessment of the following body systems: head, eyes, ears, nose, and throat; thorax; abdomen; extremities; neurological; and skin and mucosae. Any abnormalities considered by the investigator to be clinically significant are to be recorded as AEs on the AE eCRF.

Physical examination data will be presented in a listing.

Protocol 405-201-00037

10.6 **Electrocardiogram (ECG) Data**

Descriptive statistics of change from baseline in heart rate and ECG intervals of PR, QRS, QT, and QTcF, will be provided by time point and mode of administration. The incidence of potentially clinically relevant ECGs, as defined in [Appendix 3](#) will be summarized by time point and mode of administration. ECG data that are potentially clinically relevant will also be listed out by subject.

When ECG assessment is repeated, the last repeat value will be used in the summary for that visit. Unscheduled ECG value will not be summarized in the change from baseline table but will be included in incidence table.

10.7 **Potential Serious Hepatotoxicity**

A listing will be provided to present the incidence of subjects who experience an elevation in AST or ALT that is ≥ 3 times the ULN.

10.8 **Other Safety Data**

The “Baseline/Screening” version of the C-SSRS will be completed at the screening visit and the “Since Last Visit” version of the C-SSRS will be completed at check-in (Day -1 or Day 1) and EoT/ET (Day 2).

The incidence of suicidal behavior and suicidal ideation will be summarized by time point and mode of administration.

Protocol 405-201-00037

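### Does SAP 10.4 drop the Day 2 vital signs, or leave the vital-sign baseline undefined?

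*SAP*

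**What the plan says.** SAP 10.4 (Vital Sign Data) opens by saying that the vital signs "will be assessed at check-in, predose (within 2 hours before dosing) on Day 1, and 3 hours postdose on Day 1". The corresponding row of protocol Table 1.3-1 reads "Vital signs X X ^f X ^f X". The marks fall under screening, check-in, Day 1 and Day 2/EoT/ET. Footnote f is attached only to the middle two and divides Day 1 into a predose and a 3-hour reading. Protocol 8.7.3 adds that vital signs "will be collected at the time points described in the schedule of assessments".

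On the analysis, SAP 10.4 says: "Change from baseline in vital signs will be summarized for post-baseline assessment". Potentially clinically relevant values are counted by time point and mode of administration. Unscheduled readings stay out of the change-from-baseline table but count in the incidence table.

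Baseline in SAP 10.4 is the Day 1 predose reading, with this fallback: "If a parameter is missing on Day 1 then the screening data collected at check-in will be used". Protocol 9.4.2 gives a general default for all safety variables, namely the latest value before the dose.

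**The concern.** Two things look wrong on a first reading.

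**The list of times.** SAP 10.4 repeats footnote f without the table row it belongs to, so Day 2 is not mentioned. The neighbouring sections do mention it. SAP 10.3 says "Clinical hematology, chemistry, and urinalysis are tested at screening, check-in (Day -1 or Day 1), and Day 2/ET", SAP 10.5 says "A complete physical examination will be performed at screening, check-in (Day -1 or Day 1), and Day 2/ET", and SAP 10.8 names Day 2 for the C-SSRS. Vital signs are the exception. Because unscheduled readings are kept out of the change table, a programmer working from 10.4 alone might treat Day 2 as unscheduled and lose one of the two post-baseline time points. Protocol 2.3 names rises in blood pressure and heart rate as possible drug effects, so these data matter.

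**The baseline fallback.** SAP 3.1 puts screening at Day -21 to Day -2 and check-in at Day -1 or Day 1. The two do not overlap, yet the fallback sentence runs them together. The blood pressure and heart rate criteria in SAP Appendix 2 need both an extreme value and a change from baseline, so an unclear baseline could in principle alter who is flagged.

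**Working it through.** The documents state no figure to reproduce here, so the check is a count and a comparison of texts.

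**Step 1: scheduled times against named times.**

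| Time (Table 1.3-1 with footnote f) | Named in SAP 10.4? | After dosing? |
|---|---|---|
| Screening | no | no |
| Check-in | yes | no |
| Day 1 predose | yes | no |
| Day 1, 3 hours postdose | yes | yes |
| Day 2/EoT/ET | no | yes |

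Scheduled: 5. Named: 3. Not named: 5 - 3 = 2 (screening and Day 2/EoT/ET). Post-baseline: 2 scheduled, 1 named. For a subject who checks in on Day 1, the documents do not say whether one reading may serve as both check-in and predose, so the count of 5 may not apply to everyone.

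**Step 2: does leaving a time out of the list remove it from the analysis?** The opening sentence of 10.4 describes data collection. The analysis sentence covers post-baseline assessments with no restriction, and incidence is by time point. Protocol 8.7.3 defers to Table 1.3-1, where Day 2 carries its own mark. Day 2 is therefore a scheduled, post-baseline time and belongs in both tables. The rule on unscheduled readings does not reach it. Even if someone misapplied that rule, Day 2 values would still enter the incidence table, because 10.4 counts unscheduled readings there. Leaving out screening costs nothing, since 10.4 plans no separate summary of screening vital signs.

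**Step 3: which baseline does each reading of the fallback give?**

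| Data available before the dose | Check-in reading | Screening-visit reading | Protocol 9.4.2 |
|---|---|---|---|
| Predose present | predose | predose | predose |
| Predose missing, check-in present | check-in | screening | check-in |
| Predose and check-in both missing | none | screening | screening |

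The fallback refers to data taken at check-in, which is a defined visit. A value from Day -21 to Day -2 was not taken then, so the check-in reading is the natural one. It matches protocol 9.4.2 in the first two rows and parts from it only in the third. That row includes a subject who checks in on Day 1 and has nothing recorded for the parameter before the dose that day. Here a literal check-in reading gives no baseline, and protocol 9.4.2 supplies the screening value. SAP 10.3 already does the same for laboratory data.

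**Step 4: size.** At most 12 subjects are dosed once, and there is no inferential analysis. One subject in the third row is 1/12, about 8% of the trial, for one parameter in a descriptive table. The documents give no reason to expect such a case, since vital signs are planned at check-in and again shortly before the dose.

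**The case for a change.** The best argument for amending the text is that a SAP should stand on its own. Section 10.4 is the only one of the four safety sections that list assessment times (10.3, 10.4, 10.5, 10.8) to omit Day 2, which suggests a copying slip. The general baseline rule in protocol 9.4.2 is qualified as applying in general, so the specific SAP rule ought to be clear without it. SAP 10.3 shows how simply this can be worded, the repair would take two sentences, and the SAP's introduction promises that its final version will agree with the protocol.

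The textual observations stand: the list is incomplete, and the fallback wording joins two separate periods. What does not follow is any consequence. An analyst needs the protocol schedule anyway to set up visits, and with it in hand the Day 2 question does not arise. The third row of the baseline comparison is a real gap in a literal reading of 10.4, but protocol 9.4.2 fills it sensibly and no sentence in the SAP forbids that.

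**Conclusion.** No change follows. The list of times is a clerical slip, footnote text carried over without its row, and the fallback is a loosely worded sentence that the protocol's general rule resolves. An analyst working from both documents would summarise the 3-hour and Day 2 readings. The same analyst would use predose, then check-in, then screening as baseline.

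The expected effect on results is nil. At the outside, one parameter for one subject of at most 12 would lose its change from baseline, and only if both the predose and check-in values were missing and 10.4 were read literally against protocol 9.4.2.

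This rests on two assumptions: that Table 1.3-1 governs which vital signs are scheduled, as protocol 8.7.3 says, and that the general baseline rule of protocol 9.4.2 applies where the SAP wording is unclear.

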10.5 Physical Examination Data

A complete physical examination will be performed at screening, check-in (Day -1 or Day 1), and Day 2/ET. A complete physical examination will consist of measurement of height and weight and an assessment of the following body systems: head, eyes, ears, nose, and throat; thorax; abdomen; extremities; neurological; and skin and mucosae. Any abnormalities considered by the investigator to be clinically significant are to be recorded as AEs on the AE eCRF.

Physical examination data will be presented in a listing.

Protocol 405-201-00037

10.6 **Electrocardiogram (ECG) Data**

Descriptive statistics of change from baseline in heart rate and ECG intervals of PR, QRS, QT, and QTcF, will be provided by time point and mode of administration. The incidence of potentially clinically relevant ECGs, as defined in [Appendix 3](#) will be summarized by time point and mode of administration. ECG data that are potentially clinically relevant will also be listed out by subject.

When ECG assessment is repeated, the last repeat value will be used in the summary for that visit. Unscheduled ECG value will not be summarized in the change from baseline table but will be included in incidence table.

10.7 **Potential Serious Hepatotoxicity**

A listing will be provided to present the incidence of subjects who experience an elevation in AST or ALT that is ≥ 3 times the ULN.

10.8 **Other Safety Data**

The “Baseline/Screening” version of the C-SSRS will be completed at the screening visit and the “Since Last Visit” version of the C-SSRS will be completed at check-in (Day -1 or Day 1) and EoT/ET (Day 2).

The incidence of suicidal behavior and suicidal ideation will be summarized by time point and mode of administration.

Protocol 405-201-00037

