- 13) Subjects with a positive drug screen for cocaine, marijuana (even if by prescription), or other illicit drugs, or alcohol, are excluded and may not be retested or rescreened. Subjects with a positive urine drug screen resulting from the confirmed use of prescription or over-the-counter medications or products that in the investigator's documented opinion do not signal a clinical condition that would impact the safety of the subject or interpretation of the trial results may continue evaluation for the trial, following consultation and approval by the medical monitor.
- 14) The following laboratory test and ECG results are exclusionary:
 - Platelet count $\leq 130 \times 10^3/\mu\text{L}$
 - Hemoglobin $\leq 11.2 \text{ g/dL}$
 - Absolute neutrophil count $\leq 1.00 \times 10^3/\mu\text{L}$
 - White blood cell count (WBC) $\leq 4.35 \times 10^3/\mu\text{L}$
 - Aspartate aminotransferase (AST) $> 2 \times$ upper limit of normal (ULN)
 - Alanine aminotransferase (ALT) $> 2 \times$ ULN
 - Creatine phosphokinase (CPK) $> 2 \times$ ULN, unless discussed with and approved by the medical monitor
 - Creatinine $\geq 0.7 \text{ mg/dL}$
 - QT interval corrected for heart rate using Fridericia's formula (QTcF) $\geq 450 \text{ msec}$ for more than 1 of the 3 ECGs performed for subjects < 12 years old or QTcF $\geq 460 \text{ msec}$ for more than 1 of the 3 ECGs performed for subjects ≥ 12 years old.

Protocol 405-201-00037

NOTE: Subjects should be excluded if they have any other abnormal laboratory tests, vital sign results, or ECG findings which, in the investigator's judgment, are medically significant and would impact the safety of the subject or the interpretation of the trial results. Criteria will be provided to assist investigators in their assessments of results that may be potentially medically significant, depending on the subject's medical history and clinical presentation. Tests with abnormal results should be repeated to ensure reproducibility of the abnormality before excluding a subject based on the criteria noted above. The 3 ECGs done at predose should be taken at least 1 minute apart following a 10-minute rest in the supine position.

- 15) Subjects who have supine or standing diastolic blood pressure, after resting for at least 5 minutes, \geq 95 mmHg.

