8.7.4 Electrocardiogram

Electrocardiograms will be performed at the time points described in the schedule of assessments ([Table 1.3-1](#)). Subjects should be monitored for potentially clinically significant ECG results ([Section 10.7](#)). Any abnormalities considered by the investigator to be clinically significant are to be recorded as AEs on the AE eCRF.

The 12-lead ECGs will be performed in the supine position. Predose 12-lead ECGs conducted at check-in (Day -1 or Day 1) will be performed in triplicate, taken at least 1 minute apart following a 10-minute rest in the supine position. The average of the 3 values will be the baseline value. Based on the QTcF, a subject will be excluded if the correction is ≥ 450 msec for more than 1 of the 3 time points of triplicate predose ECGs performed for subjects < 12 years old or ≥ 460 msec for more than 1 of the 3 time points of triplicate predose ECGs performed for subjects ≥ 12 years old.

A central ECG service will be utilized for reading all ECGs in order to standardize interpretations for the safety analysis. In addition, ECG results will be evaluated at the trial site to monitor safety during the trial.

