Appendix 3**Criteria for Identifying ECG Measurements of Potential Clinical Relevance**

Variable	Criterion Value ^a	Change Relative to Baseline ^a
Rhythm		
Sinus tachycardia ^b	≥ 110 bpm	increase of ≥ 15 bpm
Sinus bradycardia ^c	≤ 60 bpm	decrease of ≥ 15 bpm
Supraventricular premature beat	all	not present \rightarrow present
Ventricular premature beat	all	not present \rightarrow present
Supraventricular tachycardia	all	not present \rightarrow present
Ventricular tachycardia	all	not present \rightarrow present
Atrial fibrillation	all	not present \rightarrow present
Atrial flutter	all	not present \rightarrow present
Conduction		
1 atrioventricular block	$PR \geq 200$ msec	increase of ≥ 50 msec
2 atrioventricular block	all	not present \rightarrow present
3 atrioventricular block	all	not present \rightarrow present
Left bundle-branch block	all	not present \rightarrow present
Right bundle-branch block	all	not present \rightarrow present
Pre-excitation syndrome	all	not present \rightarrow present
Other intraventricular conduction block ^d	$QRS \geq 120$ msec	increase of ≥ 20 msec
Infarction		
Acute or subacute	all	not present \rightarrow present
Old	all	not present \rightarrow present
		≥ 12 weeks post trial entry
ST/T Morphological		
Myocardial ischemia	all	not present \rightarrow present
Symmetrical T-wave inversion	all	not present \rightarrow present
Increase in QTc		
< 12 years old	$QTcF \geq 450$ msec	increase of 60 msec
≥ 12 years old	$QTcF \geq 460$ msec	from baseline

QTc = corrected QT interval.

^aThe criterion value and change relative to baseline represented in this table are intended to identify on-treatment values outside of normal changes and that could potentially be clinically relevant. In order to be identified as potentially clinically relevant, the on-treatment value must meet the “Criterion Value” and also represent a change from the subject’s baseline value of at least the magnitude shown in the “Change Relative to Baseline” column. When evaluating these values, the emotional state of the subject must be taken into consideration (eg, crying, screaming) and documented as applicable.

^bNo current diagnosis of supraventricular tachycardia, ventricular tachycardia, atrial fibrillation, atrial flutter, or other rhythm abnormality.

^cNo current diagnosis of atrial fibrillation, atrial flutter, or other rhythm abnormality.

^dNo current diagnosis of left bundle branch block or right bundle branch block.

Protocol 405-201-00037

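### Does the SAP's last-repeat rule for ECGs displace the protocol's triplicate-average baseline?

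*SAP*

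**What the plan says.** Protocol 8.7.4 sets out how the baseline ECG is obtained: "Predose 12-lead ECGs conducted at check-in (Day -1 or Day 1) will be performed in triplicate". It then defines the baseline: "The average of the 3 values will be the baseline value". The note to exclusion criterion 14 in Protocol 5.2.2 describes the same set of readings: "The 3 ECGs done at predose should be taken at least 1 minute apart following a 10-minute rest in the supine position".

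Protocol 9.4.2 gives a general baseline for safety variables, the last measurement before dosing. It qualifies this as holding in general.

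SAP 10.3 defines a laboratory baseline ("For clinical laboratory tests data, baseline is defined as the last non-missing value obtained before dosing") and SAP 10.4 a vital-sign baseline ("The baseline of vital sign is defined as data collected within 2 hours before dosing on Day 1"). SAP 10.6 plans descriptive change from baseline for heart rate, PR, QRS, QT and QTcF, and incidence of potentially relevant values under Appendix 3, but contains no definition of ECG baseline. On multiple readings it says "When ECG assessment is repeated, the last repeat value will be used in the summary for that visit". On unscheduled readings it says "Unscheduled ECG value will not be summarized in the change from baseline table but will be included in incidence table". Sections 10.3 and 10.4 carry near-identical sentences on repeats and unscheduled values.

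**The concern.** ECG is the only safety domain for which the protocol prescribes an averaged baseline, yet it is the one of these three for which the SAP states no baseline. A programmer working from the SAP alone finds a last-repeat rule. Turning to the statistics section of the protocol, the same programmer finds the general rule of the last measurement before dosing. Both point to a single reading, while the averaging rule sits in a trial-procedures section.

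If the third predose reading were taken as baseline, the change-from-baseline tables would be noisier. Appendix 3 flags that require a change from baseline could also differ between two programmers. The heart-rate flag is the more exposed, because its change criterion is only "increase of ≥ 15 bpm".

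A second question sits alongside. The SAP does not say whether an abnormal scheduled postdose value still counts in the incidence table once a repeat replaces it in that visit's summary.

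**Working it through.** **Which rule governs**

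1. SAP section 1 states that the SAP is based on the protocol and that its final version will be consistent with it. SAP 10.6 uses the word baseline without redefining it, so the protocol's definition carries over.
2. Protocol 9.4.2 is general and says so. Protocol 8.7.4 is specific to ECGs. The specific rule prevails. The general one remains a sensible fallback if a subject has no predose triplicate.
3. The note to exclusion criterion 14 asks for abnormal tests to be repeated to confirm the finding, and separately describes the 3 planned predose ECGs. Protocol 8.8.1 likewise speaks of repeating a laboratory test to verify a result. In both places a repeat is a re-test. Planned replicates are called triplicate in 8.7.4.
4. The last-repeat sentence appears in almost the same form in SAP 10.3, 10.4 and 10.6. The laboratory and vital-sign sections describe no planned replicates, so the shared sentence is most naturally about re-tests.
5. The sentence governs a visit's summary. It does not mention deriving the baseline.

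**Size if the wrong reading were used**

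The plan states no figure on this point, so there is none to reproduce, and it gives no ECG variability. Every SD below is an assumption. Let *w* be the replicate SD within a session and *b* the between-occasion SD. There is one scheduled postdose ECG, on Day 2/ET.

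- Single-reading baseline: Var(change) = 2*b*² + 2*w*²
- Mean of three: Var(change) = 2*b*² + *w*² + *w*²/3 = 2*b*² + (4/3)*w*²

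QTcF (msec):

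| *w* | *b* | SD, one reading | SD, mean of three | SD ratio | Variance ratio |
|---|---|---|---|---|---|
| 5 | 10 | √250 = 15.81 | √233.3 = 15.28 | 1.035 | 1.071 |
| 10 | 10 | √400 = 20.00 | √333.3 = 18.26 | 1.095 | 1.200 |
| 10 | 5 | √250 = 15.81 | √183.3 = 13.54 | 1.168 | 1.364 |
| 15 | 5 | √500 = 22.36 | √350 = 18.71 | 1.195 | 1.429 |
| any | 0 | √2·*w* | √(4/3)·*w* | 1.225 | 1.500 |

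The chance of a noise-only rise of 60 msec or more is 1 − Φ(60/SD). Its largest value over *w* = 5 to 15 and *b* = 5 to 10 is at *w* = 15, *b* = 10. One reading gives 1 − Φ(60/25.50) = 0.93%; the mean of three gives 1 − Φ(60/22.36) = 0.36%.

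Heart rate (bpm), noise-only rise of 15 or more, 1 − Φ(15/SD):

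| *w* | *b* | One reading | Mean of three | Difference × 12 subjects |
|---|---|---|---|---|
| 5 | 3 | SD 8.25, 3.4% | SD 7.16, 1.8% | 0.016 × 12 ≈ 0.20 |
| 5 | 5 | SD 10.00, 6.7% | SD 9.13, 5.0% | 0.017 × 12 ≈ 0.20 |
| 10 | 5 | SD 15.81, 17.1% | SD 13.54, 13.4% | 0.037 × 12 ≈ 0.45 |

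The last row is a deliberate stretch that doubles the replicate SD. All three rows are upper bounds for flagging, because the Appendix 3 sinus tachycardia flag also requires an absolute rate of at least 110 bpm.

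**The incidence table**

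SAP 10.6 confines the last-repeat rule to the visit summary and admits even unscheduled values to the incidence table. SAP 10.3, 10.4 and 10.6 also list potentially relevant values by subject. The wording leans towards counting every postdose value, and with at most 12 subjects an abnormal value that a repeat had replaced should be visible in the listing.

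**The case for a change.** The best argument for acting is that a SAP should stand on its own. This one says it documents the analysis algorithms and conventions, it defines the baseline in two neighbouring domains, and it omits the one domain with a special rule. Adding the definition would cost a few sentences and no data collection. In a trial this small a single changed flag is visible: 1/12 is 8.3 percentage points overall and, with about half the subjects in each mode of administration, 1/6 is 16.7 points within a mode. A flag can also turn on the choice. In an invented example with predose QTcF of 410, 420 and 400 msec and a postdose value of 462, the change is 52 msec from the mean and 62 msec from the last reading, on either side of the 60 msec criterion.

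The omission is real, and restating the rule would do no harm. But a divergent table requires someone to pass over an explicit protocol sentence on ECG baseline and to read re-test wording as covering planned replicates. The QTcF example is possible but was built to straddle the cut-off; under the assumed SDs, noise alone produces such a rise in fewer than 1% of subjects. How a replaced value is counted is a separate, unstated convention, which the SAP's own wording already points towards resolving inclusively.

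**Conclusion.** No change to the plan follows. SAP 10.6 leaves out a cross-reference to the protocol's ECG baseline; it neither contradicts nor replaces it. Following the two documents together gives the right baseline, the mean of the predose triplicate, with the last-repeat rule applying to re-tests.

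If the literal reading were nevertheless used, the SD of QTcF change would be about 4% to 20% larger under the assumed SDs (ceiling 22%), and the QTcF flag would hardly move. The expected number of subjects with a noise-only heart-rate rise of 15 bpm or more would go up by about 0.2 in 12 at a replicate SD of 5 bpm, and by under half a subject at 10 bpm, before the absolute rate criterion reduces it further. These sizes rest entirely on assumed variability, normal errors and one postdose ECG per subject. They concern descriptive safety tables in a trial that plans no inferential analysis; the primary endpoints, Cmax, tmax and AUC0-12h of centanafadine, do not depend on them.
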